Section 7.2 Identification of Study Cohorts	Added the following sentence: Further matching will be done on race/ethnicity (with categories being White, Black, Hispanic, Asian, and Other) if 95% of exposed individuals can be fully matched to 4 unexposed individuals. Updated matching in Figure 1 to include race/ethnicity	The amendment aligns the protocol with the SAP to reflect the inclusion of race/ethnicity as a matching variable to minimize potential bias and confounding in the study design	
Section 8.4 Sample Size and Power Estimation	Added "race/ethnicity" to the list of matching variables.	The amendment aligns the protocol with the SAP to reflect the inclusion of race/ethnicity as a matching variable	
Section 8.5 Projected Timelines	Table 7. Study timelines updated.	Timelines were updated as the cohort accrual was achieved one year earlier than planned.	

1.3 LIST OF FIGURES

Figure 1. Construction of study cohorts (Amended 17 February 2022)	22
--	----

ABBREVIATIONS

ACIP	Advisory Committee on Immunization Practices
AMI	Acute Myocardial Infarction
CI	Confidence Interval
EHR	Electronic Health Record
EMA	European Medicines Agency
FDA	Food and Drug Administration
GSK	GlaxoSmithKline Biologicals SA
HIPAA	Health Insurance Portability and Accountability Act
HR	Hazard Ratio
HZ	Herpes Zoster
HZO	Herpes Zoster Ophthalmicus
ICD	International Classification of Diseases
IRB	Institutional Review Board
KPSC	Kaiser Permanente Southern California
NLP	Natural Language Processing
PHI	Protected Health Information
PHN	Post-Herpetic Neuralgia
RCT	Randomized Controlled Trial
RIPC	Regional Immunization Practice Committee
RZV	Recombinant Zoster Vaccine
Tdap	Tetanus, diphtheria and pertussis vaccine
US	United States
VE	Vaccine Effectiveness
VZV	Varicella Zoster Virus
ZOE-50	Zoster Efficacy Study in Adults 50 Years of Age or Older
ZOE-70	Zoster Efficacy Study in Adults 70 Years of Age or Older
ZVL	Zoster Vaccine Live

209570 (EPI-ZOSTER-031 VE US)

Protocol Amendment 1

Kaiser Permanente **Research**

1. SYNOPSIS

Herpes zoster (HZ), or shingles, is an often painful vesicular rash caused by reactivation of varicella zoster virus (VZV) persisting latently in dorsal root ganglia [1, 2]. The pain from acute HZ can be disabling, and if complicated by the development of post-herpetic neuralgia (PHN), can last for months or years. Before zoster vaccine live (*Zostavax*, ZVL) was introduced, about one million episodes of HZ occurred in the United States (US) annually [3]. A study among the Medicare population showed that the effectiveness of ZVL against incidence of HZ and PHN was 48% and 59%, respectively [4]. Subsequent studies have shown the protection of ZVL wanes over time [5-7].

Recombinant zoster vaccine (*SHINGRIX*, RZV), a two-dose subunit zoster vaccine containing recombinant glycoprotein E in combination with a novel adjuvant (ASO1_B), was licensed by the Food and Drug Administration (FDA) and European Medicines Agency (EMA) in 2017. This decision was based on two large parallel Phase III randomized controlled trials (RCTs): the Zoster Efficacy Study in Adults 50 Years of Age or Older (ZOE-50) and the Zoster Efficacy Study in Adults 70 Years of Age or Older (ZOE-70). Vaccine efficacy against HZ was 97.2% in adults ages \geq 50 years in ZOE-50 and 89.8% in adults \geq 70 in ZOE-70. Vaccine efficacy against PHN was 91.2% in pooled analyses [8]. Subsequent to FDA approval for the prevention of HZ in individuals \geq 50 years of age, the Advisory Committee on Immunization Practices (ACIP) made three recommendations: (1) RZV is recommended for immunocompetent adults aged 50 years and older; (2) RZV is recommended for immunocompetent adults previously vaccinated with ZVL; and (3) RZV is the preferred vaccine over ZVL [9].

While the clinical trial data provided evidence that RZV works under ideal conditions (*i.e.*, vaccine efficacy), confirmation of these results is needed in real-world conditions (*i.e.*, vaccine effectiveness [VE]) to show whether benefits of the vaccine can be generalized to conditions of real-world clinical practice [10-12].

We will conduct a long-term, observational, cohort study in adults aged \geq 50 years at Kaiser Permanente Southern California (KPSC), a large integrated health care organization serving approximately 4.6 million racially and ethnically diverse members. Comprehensive electronic health records (EHR) at KPSC integrate all aspects of patient care, including patient demographics, diagnoses, vaccinations, medications, procedures, and laboratory results. The KPSC vaccine team has extensive experience in vaccine safety and effectiveness research and has access to EHR data in near real-time to facilitate research.

The primary objectives of the study are (1) to estimate the VE of 2 doses of RZV in preventing HZ and (2) to estimate the VE of 2 doses of RZV in preventing PHN when used in a real-world setting. HZ incidence and PHN incidence among individuals who received 2 doses of RZV will be compared to a cohort of individuals who did not receive RZV, (*i.e.*, RZV unvaccinated). Individuals will be followed until the end of their 10-year follow-up period, death, receipt of a dose of RZV among the RZV unvaccinated cohort, or termination of KPSC membership (allowing for a 31-day gap in membership), whichever comes first. For both HZ and PHN outcomes, crude VE (%) will be estimated. Adjusted hazard ratios (HRs) and 95% confidence intervals (CIs) comparing incidence in the 2-dose RZV vaccinated and RZV unvaccinated cohorts will be estimated by Cox proportional hazards regression models adjusting for potential confounders. Adjusted VE will be computed as 1-adjusted HR. Secondary analyses will be conducted to assess VE of 1 or 2 doses of RZV in various subgroups of adults ages ≥50 years, using similar methods as the primary analysis.

Kaiser Permanente **Research**

2. BACKGROUND

Herpes zoster (HZ), or shingles, is an often painful vesicular rash caused by reactivation of varicella zoster virus (VZV) persisting latently in dorsal root ganglia [1, 2]. The pain from acute HZ can be disabling, and if complicated by the development of post-herpetic neuralgia (PHN), can last for months or years. Before a vaccine was introduced, about one million episodes of HZ occurred in the United States (US) annually [3]. Aside from increasing age and immunosuppression, the other risk factors for this condition are not well known [13], but some evidence suggests sex, race / ethnicity, family history, and comorbidities may be associated with HZ [14].

Zostavax (zoster vaccine live [ZVL]), a live-attenuated vaccine prepared from the Oka/Merck strain of VZV, was licensed by the Food and Drug Administration (FDA) in 2006 and recommended by the Advisory Committee on Immunization Practices (ACIP) for healthy adults aged 60 years and older [3]. ZVL was licensed for adults aged 50-59 years in 2011, but due to ZVL shortages and waning protection, ACIP never recommended routine vaccination with ZVL in this age group. A study among the Medicare population showed that the effectiveness of ZVL against incidence of HZ and PHN is 48% and 59%, respectively [4]. Subsequent studies have shown the protection of ZVL wanes over time [5-7].

Recombinant zoster vaccine (SHINGRIX, RZV), a two-dose subunit zoster vaccine containing recombinant glycoprotein E in combination with a novel adjuvant (AS01_B), was licensed by the FDA in 2017. This decision was based on two large parallel Phase III randomized controlled trials (RCTs): the Zoster Efficacy Study in Adults 50 Years of Age or Older (ZOE-50) and the Zoster Efficacy Study in Adults 70 Years of Age or Older (ZOE-70). ZOE-50 assessed whether RZV reduced the risk of HZ in adults 50 years of age or older. During a mean follow-up of 3.2 years, HZ was confirmed in 6 out of 7,698 participants in the vaccine group and in 210 out of 7,713 participants in the placebo group (incidence rate 0.3 vs. 9.1 per 1,000 person-years). Overall vaccine efficacy against HZ was 97.2% and ranged between 96.6% and 97.9% for all age groups evaluated [15]. In ZOE-70, the overall vaccine efficacy against HZ was 89.8% (6,541 vaccinated participants and 6,622 placebo participants) and was similar in participants 70-79 years of age (90.0%) and participants 80 years of age and older (89.1%) [16]. Although these Phase III RCTs were not powered to show statistical significance in serious adverse events, there were no observed differences between subjects vaccinated with RZV and comparison populations for the overall reported rates of serious adverse events [15]. Per indication, RZV is not contraindicated in persons with immunosuppressive conditions or treatments. Subsequent to FDA approval, ACIP made three recommendations: (1) RZV is recommended for immunocompetent adults aged 50 years and older; (2) RZV is recommended for immunocompetent adults previously vaccinated with ZVL; and (3) RZV is the preferred vaccine over ZVL [9].

While the clinical trial data provided evidence that RZV works under ideal conditions (*i.e.*, vaccine efficacy), confirmation of these results is needed in field conditions (*i.e.*, VE including storage and handling) to show whether benefits of the vaccine can be generalized to conditions of clinical practice [10-12]. This is particularly important for RZV, given that the elderly population for whom the vaccine is indicated often has multiple comorbidities. Moreover, a large observational study allows for exploration of vaccine benefits and durability of protection among important patient subgroups that would be infeasible in most RCTs. With our experience in HZ and HZ vaccine [7, 17-30], Kaiser Permanente Southern California (KPSC) will conduct an RZV effectiveness study in the US.

Kaiser Permanente **Research**

3. STUDY OBJECTIVES

We will conduct a study to assess VE among individuals at KPSC who received RZV ("vaccinated") compared to individuals who did not receive RZV ("RZV unvaccinated") with 10 years of follow-up, addressing the objectives below.

Although RZV should be administered as 2 doses separated by 2-6 months, ACIP guidance followed at KPSC specifies that a second dose administered <4 weeks after the first dose should be repeated, but a second dose administered ≥4 weeks after the first dose not need to be repeated [9]. Furthermore, due to variation in real-world practice, the second dose may be given earlier than 2 months after the first dose. Therefore, objectives refer to 2 doses of RZV given 4 weeks to 6 months apart, except where indicated otherwise (secondary objectives 8-9 and exploratory objective 1).

Primary objectives:

- 1. To estimate the VE of 2 doses of RZV in preventing HZ in adults aged ≥ 50 years
- 2. To estimate the VE of 2 doses of RZV in preventing PHN in adults aged ≥ 50 years

Secondary objectives:

- 1. To estimate the VE of 2 doses of RZV in preventing HZ in adults aged ≥ 50 years by age, by sex, and by race/ethnicity
- 2. To estimate the VE of 2 doses of RZV in preventing PHN in adults aged ≥ 50 years stratified by age, by sex, and by race/ethnicity
- 3. To estimate the VE of 2 doses of RZV in preventing HZ in adults aged ≥ 50 years, by prevalent comorbidities at baseline (kidney disease, heart disease, lung disease, liver disease, diabetes)
- 4. To estimate the VE of 2 doses of RZV in preventing HZ in adults aged \geq 50 years, by history of ZVL
- 5. To calculate the incidence of HZ in vaccinated (2 doses of RZV) and RZV unvaccinated adults ≥ 50 years, by prior history of HZ
- 6. To estimate the VE of 2 doses of RZV in preventing herpes zoster ophthalmicus (HZO) in adults aged ≥ 50 years
- 7. To estimate the VE of 2 doses of RZV in preventing hospitalized acute myocardial infarction (AMI), and hospitalized stroke in adults aged ≥ 50 years
- 8. To estimate the VE of 1 dose of RZV in preventing HZ in adults aged \geq 50 years
- 9. To estimate the VE of 1 dose of RZV in preventing PHN in adults aged ≥ 50 years

Exploratory objectives:

- 1. To estimate the VE of 2 doses of RZV in preventing HZ and PHN, when the second dose is received more than 6 months after the first dose in adults aged ≥ 50 years
- To estimate the VE of 2 doses of RZV in preventing HZ, by presence of concomitant vaccination (*e.g.,* receipt of influenza vaccine, pneumococcal vaccine, or tetanus, diphtheria and pertussis vaccine [Tdap]) at the time of receiving either the first or second dose of RZV) in adults aged ≥ 50 years

- 3. To assess clinical characteristics associated with the acute HZ episode for a sample of cases (100 RZV vaccinated [2-dose] HZ cases and 100 RZV unvaccinated HZ cases) in adults aged ≥ 50 years
- 4. To estimate the VE of 2 doses of RZV in preventing HZ-related meningoencephalitis and bacterial superinfection in adults aged ≥ 50 years
- To estimate the relative risk of disseminated HZ among vaccinated (2 doses of RZV) and RZV unvaccinated adults ≥ 50 years who are immunocompromised at the time of their incident HZ diagnosis

Kaiser Permanente **Research**

4. RESEARCH INSTITUTION OVERVIEW

4.1 Study Setting

Kaiser Permanente is one of the nation's largest not-for-profit health plans. As an integrated health care system, KPSC provides an ideal environment for population-based research. The health plan's population includes more than 4.6 million members who represent 260 different ethnicities and speak more than 150 different languages. The demographic makeup of the KPSC membership closely mirrors the Southern California population [31] and the California census population. Compared to the racial/ethnic distribution of the US population, KPSC membership is comprised of twice as many individuals of Asian/Pacific Island descent and three times as many Hispanic individuals.

KPSC facilities include hospitals and medical offices, all linked by an information infrastructure that supports both clinical practice and business needs. Health information from this infrastructure can be leveraged for research purposes. More than 90 percent of members remain in the health plan after one year; more than three-quarters remain after three years. The large, diverse, and stable population permits the rapid accrual of a representative sample size and offers the ability to evaluate long-term implications of immunization.

KPSC began administering ZVL in late 2006 when it was first recommended by the ACIP and KPSC Regional Immunization Practice Committee (RIPC). As of January 1, 2018, over 380,000 doses of ZVL had been administered. In 2017, ACIP recommended RZV preferentially over ZVL. As of April 2018, RZV is the preferred HZ vaccine for routine use and the standard care for the prevention of HZ in adults aged 50 years and older at KPSC. As of April 30, 2019, 60,481 individuals have received at least 1 dose of RZV and 26,887 have received 2 doses, despite limited supply of RZV that has since increased.

4.2 Electronic Health Records

Kaiser Permanente Health Connect is the largest and most advanced civilian electronic health record (EHR) system available in the US. In addition to supporting patient care, this robust system facilitates research, providing access to EHR for the KPSC vaccine research team. Up-to-date details of patient care are available and accessible to researchers. Data regarding demographics, services, and diagnoses are tracked from the outpatient, Emergency Department and hospital settings.

Pharmacy and vaccination utilization are linked through patients' unique medical record numbers. As KPSC is a pre-paid health care system, recommended vaccines such as RZV are provided to KPSC members at no charge and can be obtained at no-cost nurse visits or on a walk-in basis without appointment, which is an incentive for members to receive immunizations within the system. Vaccinations received outside of the health plan with appropriate documentation are also recorded in KPSC databases.

KPSC members have very strong motivation to use services internally. For outside providers to be reimbursed by the health plan for covered emergent or contract care, claims must be submitted with documentation of the episode of care, which is integrated into administrative data systems. Thus, the

capture of care is considered to be very comprehensive. Care received at KPSC is updated and available to researchers in near real time. Claims data are over 90% complete after 3 months.

4.3 Study Population Demographics

As of January 1, 2018, KPSC membership consisted of 1,495,838 KPSC members aged 50 years and older, 899,592 members aged 60 years and older, and more than 130,000 members aged 80 years and older (Table 1). Approximately 53% of KPSC members were female, and the racial/ethnic composition included White (43%), Hispanic (30%), Asian/Pacific Islander (11%), and African American (9%). Geographically, KPSC covers the entire Southern California region from Bakersfield to San Diego.

Age on January 1, 2018 (years)	Frequency	Percent
50-59	596,246	39.86
60-69	493,190	32.97
70-79	275,722	18.43
80+	130,680	8.74
Sex		
Female	793,381	53.04
Male	702,457	46.96
Race/Ethnicity ¹		
White	636,438	42.55
Hispanic	452,243	30.23
Asian and Pacific Islander	167,298	11.18
African American	138,879	9.28
Multiple/other/unknown	100,980	6.75
Total	1,495,838	100
¹ All categories other than Hispanic are no	n-Hispanic ethnicity.	

Table 1. Demographic distribution of KPSC members 50 years and older on January 1, 2018

Table 2 shows the length of retention of KPSC membership by age group beginning January 1, 2008. Approximately 52% of members aged 50-59, 61% of members aged 60-69 years, and 57% of members aged 70-79 years had completed 10 years of membership at KPSC. For members aged 80 years and older, the percentage of members who completed 10 years of membership at KPSC decreased to 24%. The stability of KPSC membership allows the unique opportunity to follow patients over time and conduct long-term effectiveness studies.

		Membership length (years)			
		0-5	>5-10	>10	Total
Age on January 1, 2008 (years)					
	Ν	145,613	77,164	239,563	462,340
20-23	Row %	31.49	16.69	51.82	
60.60	Ν	76,378	37,055	176,036	289,469
60-69	Row %	26.39	12.8	60.81	
70.70	Ν	33,640	34,072	88,441	156,153
70-79	Row %	21.54	21.82	56.64	
201	Ν	34,335	23,808	18309	76,452
00+	Row %	44.91	31.14	23.95	
Total	Frequency	289,966	172,099	522,349	984,414

Table 2. Prospective length of KPSC membership among individuals aged ≥50 years on January 1, 2008

Kaiser Permanente **Research**

5. STUDY DESIGN OVERVIEW

We will conduct a long-term, observational cohort study in adults aged \geq 50 years at KPSC with primary objectives of (1) estimating the VE of 2 doses of RZV in preventing HZ and (2) estimating the VE of 2 doses of RZV in preventing PHN.

A cohort design is ideal to examine multiple outcomes, estimate annual VE and evaluate waning effectiveness, and observe rare events (*e.g.*, breakthrough HZ, PHN, HZO), taking advantage of the EHR system at KPSC. For the primary analyses, HZ incidence and PHN incidence among individuals who received 2 doses of RZV separated by 4 weeks to 6 months will be compared to a cohort of individuals who did not receive RZV (*i.e.*, RZV unvaccinated). Individuals will be followed until the end of their 10-year follow-up period, death, receipt of a dose of RZV among the RZV unvaccinated cohort, termination of KPSC membership (allowing for a 31-day gap in membership), or occurrence of event of interest (for event-specific analyses), whichever comes first. Additional analyses will be conducted to address the secondary and exploratory objectives exploring the VE of 1 or 2 doses of RZV in various subgroups.

The study will be conducted in accordance with regulations and guidelines from the International Society for Pharmacoepidemiology Guidelines for Good Pharmacoepidemiology Practices (GPP), International Epidemiological Association Guidance on Good Epidemiological Practice (GEP), and the Council for International Organizations of Medical Sciences International Ethical Guidelines for Epidemiological Studies (CIOMS). [32-34]

Kaiser Permanente **Research**

6. MEASURES

6.1 Exposure Definitions

We will identify RZV vaccinations from the EHR, which is available and accessible in real-time, providing the ability to view vaccine details and collect patient immunization history at the point of care. Since the EHR captures the dates the vaccinations were given, we are able to determine the dose sequence based on the dates.

The index dose will be defined as the second RZV dose received 4 weeks to 6 months after the first dose for primary objectives 1-2, secondary objectives 1-7, and exploratory objectives 2-5. The index dose will be defined as the first RZV dose for secondary objectives 8-9. The index dose will be defined as the second RZV dose received more than 6 months after the first dose for exploratory objective 1. The index date corresponds to the index dose for the respective objectives.

6.1.1 Exposure for primary objectives

The exposure of interest for primary objectives 1-2 is receipt of 2 doses of RZV, with the second dose received 4 weeks to 6 months after the first dose.

6.1.2 Exposure for secondary objectives

The exposure of interest for secondary objectives 1-7 is receipt of 2 doses of RZV, with the second dose received 4 weeks to 6 months after the first dose. The exposure of interest for secondary objectives 8-9 is receipt of 1 dose of RZV.

6.1.3 Exposure for exploratory objectives

The exposure of interest for exploratory objective 1 is 2 doses of RZV, with the second dose received more than 6 months after the first dose. The exposure of interest for exploratory objectives 2-5 is 2 doses of RZV, with the second dose received 4 weeks to 6 months after the first dose.

6.2 Outcome Definitions

6.2.1 Identification of HZ

HZ will be defined by International Classification of Diseases (ICD)-10 codes (B02.xx) from hospital, outpatient, and Emergency Department settings with an antiviral prescription (acyclovir, valacyclovir, famciclovir) within 7 days before or after the date of HZ diagnosis. Inclusion of an antiviral prescription as part of the HZ definition ensures identification of new HZ diagnoses, rather than carry-over codes from prior HZ episodes.

6.2.2 Identification of PHN

PHN will be defined as HZ-related pain persisting >3 months after HZ diagnosis [35]. HZ-related pain will be defined as pain consistent with the HZ episode which is not explained by other obvious causes (e.g., rheumatoid arthritis). We will use targeted chart review to identify PHN from encounters in the >3- to 6-month period after HZ diagnosis.

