6.2.3 Identification of other outcomes

Secondary and exploratory objectives, described further in Sections 0 and 0 respectively, include the following outcomes:

- HZO during the follow-up period will be identified using natural language processing (NLP) of EHR notes, as described in our previous study [36].
- Hospitalized AMI will be identified by ICD-10 codes from inpatient encounters, or Emergency Department encounters if the patient was hospitalized or if the patient died the same or next day.
- Hospitalized stroke will be identified by ICD-10 codes from inpatient encounters, or Emergency Department encounters if the patient was hospitalized or if the patient died the same or next day.
- Characteristics of the clinical presentation of the initial acute HZ episode will be identified from chart review.
- HZ-related meningoencephalitis will be identified by targeted chart review of inpatient encounters with ICD-10 codes and/or cerebrospinal fluid (CSF) test results positive for VZV.
- HZ-related bacterial superinfection will be identified by ICD-10 codes and antibiotic prescriptions.
- Disseminated HZ will be identified by targeted chart review of EHR of vaccinated and unvaccinated individuals who are immunocompromised at the time of their incident HZ diagnosis.

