Similarly, to calculate the crude VE for preventing PHN by follow-up year after vaccination, the number of PHN cases occurring within that year and the number of person-years of follow-up for subjects in that year will be assessed for the 2-dose (4 weeks to 6 months) RZV cohort and the matched unvaccinated cohort. Crude VE (%) will be estimated as (1 – [incidence of PHN among the 2-dose (4 weeks to 6 months) RZV vaccine recipients / incidence of PHN among RZV unvaccinated individuals]) x 100. The adjusted HRs and 95% CIs comparing PHN incidence in the 2-dose (4 weeks to 6 months) RZV cohort and the matched unvaccinated cohort will be estimated by Cox proportional hazards regression models adjusting for potential confounders (Section 0). In addition, for primary objective 2, adjusted relative risks for PHN among HZ cases that were 2-dose (4 weeks to 6 months) RZV vaccine recipients compared to RZV unvaccinated HZ cases will be calculated using Poisson regression with robust error variance [37]. Matching will be broken for this analysis.

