9. DATA MANAGEMENT AND DATA QUALITY

Data management activities will be performed by KPSC. The KPSC EHR will be the data source for extracting information on exposures, outcomes, and covariates. KPSC will develop the study datasets, maintain documentation, and perform data quality checks.

Programmers will extract data per protocol and reference documentation for KPSC EHR databases. They will conduct data quality checks which includes data integrity control, double programming, and program review. Data integrity control will include checks such as sample size, duplications, formatting, etc. Double programming (i.e., programming independently conducted by 2 people) will be performed on the cohort extraction as well as key outcome variables. The results of the original and validation programming will be compared, discrepancies will be investigated, and action will be taken to resolve discrepancies. Program review (i.e. a second person reviews the code of the lead programmer) will be performed on all programs that are not double-programmed. All decisions made during data extraction and data quality checks will be documented in a programming decision log.

Kaiser Permanente **Research**

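### PHN depends on a chart reader's attribution of pain, and the protocol does not say that readers are masked to RZV status

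*Supplement*

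**What the plan says.** Primary objective 2 (section 3) is "To estimate the VE of 2 doses of RZV in preventing PHN in adults aged ≥ 50 years". HZ itself is found from a diagnosis code plus an antiviral prescription (6.2.1). PHN is not coded. Section 6.2.2 defines HZ-related pain as "pain consistent with the HZ episode which is not explained by other obvious causes" and gives the method: "We will use targeted chart review to identify PHN from encounters in the >3- to 6-month period after HZ diagnosis".

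On where RZV status is held, section 6.1 describes the EHR as "providing the ability to view vaccine details and collect patient immunization history at the point of care", and section 9 says: "The KPSC EHR will be the data source for extracting information on exposures, outcomes, and covariates".

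PHN enters two analyses in section 8.1. One is the Cox model for PHN VE. The other is an additional Poisson model for "adjusted relative risks for PHN among HZ cases that were 2-dose (4 weeks to 6 months) RZV vaccine recipients compared to RZV unvaccinated HZ cases".

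Disseminated HZ (exploratory objective 5) is ascertained in a similar way: "Disseminated HZ will be identified by targeted chart review of EHR of vaccinated and unvaccinated individuals" (6.2.3).

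The quality controls in section 9 are data integrity checks, double programming and program review. No section mentions masking of chart readers, a second reading, adjudication or a check of agreement.

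**The concern.** Whether pain three to six months after a rash is residual zoster pain or has another cause is a judgement. A reader who knows that a case is a breakthrough after RZV may more readily put the pain down to something else, or may look harder for PHN. Either error differs by exposure group, so it does not cancel in a ratio.

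Section 11 treats misclassification as a problem only when it differs between exposure groups. It discusses this for HZ alone, and its remedy is a covariate for prior health care use. That covariate cannot correct a reader's knowledge of RZV status, nor can any other variable in section 6.3. Double programming verifies code, not the attribution of pain.

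At stake is mainly the claim about whether vaccinated people who still develop HZ have a lower risk of PHN. That comparison starts from HZ cases in both groups, so there is no large protective effect against HZ to dilute a reader's error.

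**Working it through.** **Inputs from section 8.4.** Unvaccinated rates of 10 HZ and 1.0 PHN per 1,000 person-years (so 10% of HZ cases develop PHN); censoring of 7% (vaccinated) and 15% (unvaccinated) per year; 4:1 matching; 10 years; target 2-dose cohort 89,785.

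**The plan's own figure.** A Lakatos log-rank calculation (two-sided 0.05, 80% power, HR 0.4, 5 years) gives 5,853 vaccinated against the stated 5,836, and 5,836/0.065 = 89,785. The sizing is not in dispute. It supplies the counts below.

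**Assumption, not from the documents.** Readers accept PHN in vaccinated cases at k = 0.8-0.9 times the rate for identical unvaccinated cases.

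**1. Shift in PHN VE.** Observed VE = 1 − k(1 − VE).
- VE 90%: 1 − 0.9 × 0.10 = 91%; 1 − 0.8 × 0.10 = 92%
- VE 80%: 1 − 0.9 × 0.20 = 82%; 1 − 0.8 × 0.20 = 84%
- VE 60%: 1 − 0.9 × 0.40 = 64%; 1 − 0.8 × 0.40 = 68%

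**2. Shift in the relative risk among HZ cases.** Observed RR = k × true RR, so a true 1.0 reads as 0.9-0.8.

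**3. That shift against sampling error, at 90% VE.**
- Mean person-years over 10 years, with hazard −ln(1 − c): (1 − 0.93^10)/0.0726 = 7.11 vaccinated; (1 − 0.85^10)/0.1625 = 4.94 unvaccinated.
- Vaccinated PHN: 89,785 × 7.11 × 0.010 × 0.1 × 0.1 = 64.
- Unvaccinated PHN: 4 × 89,785 = 359,140; 359,140 × 4.94 × 0.010 × 0.1 ≈ 1,775.
- SE(log RR) = √(1/64 + 1/1,775) = 0.127.
- ln 0.9 = −0.105, or 0.8 SE; ln 0.8 = −0.223, or 1.75 SE.

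Subtracting the reciprocals of the HZ counts (about 640 and 17,750), as a risk ratio among HZ cases requires, gives an SE of 0.121 and a shift of 0.9-1.8 SE. The difference is small.

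**4. False-positive rate when the true RR is 1.** Here the censoring figures were taken directly as hazards, giving about 643 vaccinated and 17,914 unvaccinated HZ cases at 90% VE, with an unadjusted normal approximation for log RR. The chance of two-sided p < 0.05 rises from 5% to 13% with 10% under-calling and to 38% with 20%. At 70% VE, where there are more vaccinated cases, the figures are 28% and 79%.

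**5. The opposite direction.** If readers over-call PHN in vaccinated cases by 10-20%, a true RR of 1.0 reads as 1.1-1.2, and a PHN VE of 90% reads as 1 − 1.1 × 0.10 = 89% to 1 − 1.2 × 0.10 = 88%.

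**The case against.** The strongest reply is that silence is not absence. A SAP exists (the amendment rationale refers to it) but was not among the documents reviewed, and a SAP or abstraction manual may describe masking. It is also an inference that abstractors see RZV status. Section 6.1 describes how exposure is identified, section 9 names a common data source, and section 6.2.2 already confines the review to encounters in a set window. This stands: the documents support the statement that no masking is stated, and no more. It does not dispose of the point, because the protocol itself sets the PHN definition, the way PHN is found and the quality controls, and masking belongs beside them.

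A reader might also infer that the group is known before the chart is opened, because section 8.3 draws samples by vaccination group for exploratory objectives 3 and 5. That does not follow. A programmer can draw 100 per group without passing on the flag.

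Nor do the documents support the inference that any bias must favour the vaccine. Closer scrutiny of breakthrough cases would lower the estimated VE.

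Finally, PHN VE rests largely on HZ counts that no PHN reader touches, and the relative risk among HZ cases is an additional analysis. Both are true, and they limit the size of the concern to what is shown in the working.

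**Conclusion.** The concern holds in a limited form. A primary outcome depends on a reader's judgement, the record system holds exposure status, and the protocol states no safeguard between the two. The main exposure is the adjusted relative risk of PHN among HZ cases: 10-20% under-calling in vaccinated cases would move a true 1.0 to 0.9-0.8, or 0.8-1.75 SE at 90% VE. PHN VE would move by 1-2 points at 90%, 2-4 at 80% and 4-8 at 60%.

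These sizes rest on an assumed reader error, on a 10% PHN risk among HZ cases in both groups, and on the plan's own rates, censoring and target cohort. The documents do not show that readers are unmasked, that they err at all, or in which direction they would err. The point is worth acting on because the safeguard is cheap and no later adjustment can replace it.

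**What to change.** State in 6.2.2, and for disseminated HZ in 6.2.3, that:
- the programmer issues review lists in random order, with vaccinated and unvaccinated cases mixed and no cohort flag;
- readers work from the encounter notes in the stated window, with immunization records and vaccine orders withheld;
- readers record on the abstraction form whether a note nevertheless revealed RZV status.

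Report the frequency of unmasking by group as a description only. Do not restrict the PHN analysis to cases that stayed masked. Mentions of RZV depend on vaccination, and people with lasting pain are likely to have more notes, so the restriction could preferentially drop vaccinated PHN cases and itself bias the relative risk.

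The cost is programming of the lists and extract plus one form field. No extra reader is needed and the sample size does not change. Masking will be incomplete where free text mentions the vaccine. There is time: under section 8.5, follow-up runs to December 2030 and the formal analyses are reserved for the final report in October 2032. If readers are already masked in practice, a sentence in 6.2.2 saying so would settle the main point.
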